## 12.3 Withdrawal from the Study (Early Termination)

Volunteers may be withdrawn from the study permanently for the following reasons:

- 1. Volunteers may withdraw from the study at any time if they wish, for any reason.
- 2. The principal investigator or designee has reason to believe that the volunteer is not complying with the protocol.
- 3. If the sponsor decides to terminate or suspend the study.

If the volunteer withdraws from the study, all early termination visit procedures will be performed according to the Schedule of Procedures (Appendices A, B and C) where possible. Every effort will be made to determine and document the reason for withdrawal from the study.

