## 5.0

## STUDY ENDPOINTS AND STUDY DESIGN

## 5.1 Study Endpoints

## 5.1.1 Primary Endpoints

Safety and tolerability:

- Proportion of volunteers with solicited adverse events (any OR any grade 3 or above) during a 14 day (Day 0 to Day 14) follow-up period after each vaccination
- Proportion of volunteers with unsolicited adverse events (any OR any grade 3 or above OR any related event OR any grade 3 or above and related) during a 4 week (Day 0 to Day 28) follow-up period after each vaccination and over the whole vaccination period

- Proportion of volunteers with abnormal biochemical and haematological values (any grade 3 or above) after each vaccination and throughout the study period
- Proportion of volunteers with serious adverse events (any event OR any related event) throughout the study period

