## 6.6 Final Visit/Early Termination Visit

Assessments and procedures will be performed according to the Schedule of Procedures (Appendices A, B and C). Volunteers will be offered participation in the IAVI Long-Term Follow-Up protocol.

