# 20.0 ETHICAL CONSIDERATIONS

The Principal Investigator will ensure that the study is conducted in compliance with the protocol, Standard Operating Procedures in accordance with guidelines laid down by the International Conference on Harmonisation for Good Clinical Practice in clinical studies, the ethical principles that have their origins in the Declaration of Helsinki and applicable regulatory requirements.

In addition to IEC/IRB and regulatory approvals, all other required approvals will be obtained before recruitment of volunteers.

Visits for Group								G	roups	A and	В							
Month	Screen	M0 Enrol				M 1				M2	M4				M5	М9	M12	M16/ ET 
Week		0		W1	W2	W4	W4+ D3	W5	W6	W8	W16	W16 +D3	W17	W18	W20	W36	W48	W64
Study Day		0	D3	D7	D14	D28	D31	D35	D42	D56	D112	D115	D119	D126	D140	D252	D336	D448
Visit Windows (Days)		-42 	± 1	± 2	± 3	± 3	± 1	± 2	± 3	± 3	± 3	±1	± 2	± 3	± 3	±7	±7	±7
Investigational Product																		
Investigational Regimen A/B or Placebo		x				x					X							
Consent /Questionnaires/Counseling																		
Informed Consent and Assessment of Understanding	х																	
Screening Questionnaire	х																	
HIV Risk Assessment 	х	Х													х			Х
Social Impact Questionnaire																		Х
HIV Risk Reduction Counseling	х	Х				X					X				х	х	х	х
Pre-/Post HIV-test Counseling	х	Х				Х					X				х	х	х	х
Family Planning Counseling	Х	Х				Х					X				Х	Х	х	Х
Clinical Safety Assessments						-									•			
Comprehensive Medical History	х																	
Interim Medical History		Х	Х	Х	Х	Х	Х	Х	Х	х	X	х	х	х	Х	х	х	х
Concomitant Medications	х	X	х	х	х	x	х	х	х	х	x	х	х	х	х	х	х	х
General Physical Exam	х																	х
Symptom-Directed Physical Exam		Х	х	х	Х	х	х	х	Х	х	X	х	х	х	х	х	х	
Weight & Height	Х																	х
Ophthalmic examination 	Х																	х

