# APPENDIX A: SCHEDULE OF PROCEDURES—GROUPS A and B

IAVI Protocol B002 Version: 4.0 Date: 3 Aug 2010 Page 58 of 95

Visits for Group								G	roups	A and	В							
Month	Screen	M0 Enrol				M 1				M2	M4				M5	М9	M12	M16/ ET 
Week		0		W1	W2	W4	W4+ D3	W5	W6	W8	W16	W16 +D3	W17	W18	W20	W36	W48	W64
Study Day		0	D3	D7	D14	D28	D31	D35	D42	D56	D112	D115	D119	D126	D140	D252	D336	D448
Visit Windows (Days)		-42 	±1	± 2	± 3	± 3	±1	± 2	± 3	± 3	± 3	±1	± 2	± 3	± 3	±7	±7	±7
Investigational Product																		
Investigational Regimen A/B or Placebo		Х				x					x							
Clinical Safety Assessments cont'd												•		•		•	•	
Vital Signs	Х	X 				X 					X 							
Local and Systemic Reactogenicity		X 	Х	х	Х	X 	х	х	Х		X 	Х	х	Х				
Adverse Events		Х	Х	Х	Х	Х	х	Х	Х	Х	X	х	х	х	Х	Х		
Serious Adverse Events	X 	Х	Х	х	Х	Х	х	х	Х	Х	Х	х	Х	х	Х	Х	х	Х
Lab Samples							•							 		 	 	
HIV test 6	х	Х				X					X				х	x	x	x
Hep BsAg, anti-HepC, active syphilis and active tuberculosis  (Chest x-ray and sputum)	x																	
Haematology (+ plasma storage  )	Х	Х		Х		Х		Х		Х	X		х		Х	Х		Х
Clinical Chemistry (+ serum storage  )	Х	Х		Х		Х		Х		Х	X		х		Х	Х		Х
Immunology (CD4, CD8)		Х																Х
Urinalysis	Х	Х			Х	Х			Х		X			х				Х
Pregnancy Test (all female volunteers)	x	x				x					x						x	x
Immunology Lab																		
Ad35 neutralization antibody assay (anti-vector) 	x	x													x			x
Sample HLA Typing 		х																

Visits for Group								G	roups	A and	В							
Month	Screen	M0 Enrol				M1				M2	M4				M5	M9	M12	M16/ ET 
Week		0		W1	W2	W4	W4+ D3	W5	W6	W8	W16	W16 +D3	W17	W18	W20	W36	W48	W64
Study Day		0	D3	D7	D14	D28	D31	D35	D42	D56	D112	D115	D119	D126	D140	D252	D336	D448
Visit Windows (Days)		-42 	± 1	± 2	± 3	± 3	± 1	± 2	±3	± 3	± 3	±1	± 2	± 3	±3	± 7	±7	±7
Investigational Product																		
Investigational Regimen A/B or Placebo		Х				X					X							
Immunology Lab cont'd																		
PBMCs for Cellular immunogenicity assays, QA  + PBMC storage  - ELISPOT 	X 	x								x	x				x			x
- ICS 		X							x	x	x				х			х
Exploratory cellular immunology assays 		х								х	х				х			х

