Antibody Immunogenicity Assays (anti-HIV) 		Х								х	x				х			x
Other																		
Refer to IAVI Long Term Follow -Up Protocol																		x

 = Early Termination

-  = Allowable window for screening for Ad35 antibodies and collection of PBMCs from first 10 volunteers screened is -90 days; all other screening procedures is -42 days.
-  = Exam will be performed on 50% of enrolled volunteers at specified centres. First exam must be performed prior to first vaccination. Second exam must be performed within 1 month after final study visit.
-  = At baseline and 30 min post vaccination
-  = Only serious events that are related to study procedures will be collected during screening period
-  = If HIV infected, perform Early Termination visit and refer volunteer to IAVI Protocol H
- = Chest X-ray and sputum examination for Acid Fast Bacilli will be performed for volunteers presenting with productive cough of more than 15 days duration to rule out active tuberculosis

-  = Further details are in the Laboratory Analytical Plan. Stored serum and plasma will be split between IAVI Human Immunology Laboratory (HIL) and GSK Laboratory. Stored PBMC will be split between IAVI HIL and GSK for exploratory research objectives on cells.
-  = Testing will be conducted at IAVI HIL
-  =Testing will be contracted out to a qualified HLA typing laboratory and performed in volunteers with robust immune responses in order to map T cell epitopes
- =Immunogenicity testing (ELISPOT) will be conducted at CRCs, where feasible, and at IAVI HIL
-  = Immunogenicity testing (ICS) will be conducted at GSK laboratories
-  = Immunogenicity testing (Exploratory cellular immunology) will be conducted at CRCs, where feasible, and at IAVI HIL or at GSK laboratories
-  = Serology against clade B antigens will be done at GSK laboratories. Serology to multiple clades will be performed at sites on a subset of subjects/time-points
-  =PBMCs will be collected from first 10 volunteers screened at each clinical research centre for purposes of standardization, quality control, and future assays related to HIV vaccine research and development
-  =HIV risk assessment at screening will determine eligibility. A separate HIV risk assessment questionnaire will be administered after enrolment.

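### The early termination visit uses the month 16 column, so a volunteer who exits inside an open safety window has no scheduled collection of solicited or non-serious unsolicited events

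*Protocol*

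**What the plan says.** **Content of the ET visit.** Section 12.3 refers to the schedule: "all early termination visit procedures will be performed according to the Schedule of Procedures (Appendices A, B and C) where possible". Section 6.6 does the same and adds no safety procedure: "Assessments and procedures will be performed according to the Schedule of Procedures (Appendices A, B and C). Volunteers will be offered participation in the IAVI" (the rest of that sentence names a separate long-term study).

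**The schedule.** In Appendices A (Groups A and B), B (Group C) and C (Group D), ET is one column with M16 (W64, D448). The footnote to that column only spells out the abbreviation, "Early Termination". The rows "Local and Systemic Reactogenicity" and "Adverse Events" are blank there. The row "Serious Adverse Events" is marked, as are "Interim Medical History", concomitant medications, general physical examination, haematology, clinical chemistry and urinalysis.

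**Collection times.** Sections 9.1.1 and 9.1.2 (solicited local and systemic events) and 9.1.4 (other adverse events) tie collection to the time points in these appendices. Section 6.3 places memory card review at the Day 3, 7 and 14 visits.

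**Endpoints.** Section 5.1.1 lists as primary: "Proportion of volunteers with solicited adverse events (any OR any grade 3 or above) during a 14 day (Day 0 to Day 14", after each vaccination. It also lists unsolicited events to Day 28 after each vaccination and over the whole vaccination period.

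**The concern.** Blank cells suit a completer at month 16, 48 weeks after the last dose, when every solicited and unsolicited window has closed. They do not suit someone who leaves days after a dose. That person is in the clinic with a primary endpoint window still open, yet the schedule asks neither the solicited-event questions nor the open adverse event question.

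Such exits are foreseeable:

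- Section 12.3 lets volunteers leave at any time for any reason.
- Section 12.3 also lists sponsor termination or suspension, which could follow a safety review under section 17.3.
- Section 11.3.2 and footnote 6 of the appendices send a volunteer with confirmed HIV infection to the ET visit. HIV samples are drawn on dosing days after enrolment (D28 and D112 in Groups A, B and D; D84 and D112 in Group C), so a result can arrive while a window is open.

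Section 14.2.1 bases the safety analysis on within-group incidence rates. An uncollected event therefore goes straight into the reported figure.

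**Working it through.** **Step 1. Read the rows against the 18 schedule columns.**

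| Row | Groups A, B, D | Group C | M16/ET |
|---|---|---|---|
| Reactogenicity | D0, 3, 7, 14; D28, 31, 35, 42; D112, 115, 119, 126 | D0, 3, 7, 14; D84, 87, 91, 98; D112, 115, 119, 126 | blank |
| Adverse events | 15 marks, D0 to D252 | 15 marks, D0 to D252 | blank |
| Serious adverse events | every visit | every visit | marked |

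**Step 2. Compare the primary safety endpoints with the ET column.**

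- Solicited events to Day 14: not scheduled at ET.
- Unsolicited events to Day 28 and over the vaccination period: not scheduled at ET, except serious ones.
- Grade 3 or higher laboratory values: haematology and chemistry are marked at ET.
- Serious adverse events: marked at ET.

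Two of the four are covered. Two are not, apart from serious events.

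**Step 3. Longest stretch without structured collection for one leaver (nominal days, ignoring visit tolerances).**

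- Solicited window: D7 to D14 after a dose, 14 − 7 = 7 days.
- Unsolicited window: D14 to D28 after a dose, 28 − 14 = 14 days.
- Vaccination period: D56 to D112 in Groups A, B and D, 112 − 56 = 56 days; D28 to D84 in Group C, 84 − 28 = 56 days.

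**Step 4. Number of leavers.** The protocol gives no drop-out rate. Assume 3 to 5% of 28 vaccinees: 0.84 to 1.40 per group. Assume also that exits spread evenly over 448 days.

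- Solicited windows: 3 × 14 = 42 days; 42/448 = 9.4%; 0.08 to 0.13 leavers per group.
- 28-day windows: 3 × 28 = 84 days; 84/448 = 18.75%; 0.16 to 0.26 per group, or 0.63 to 1.05 over four groups.
- Vaccination period, taken here as D0 to D140: 140/448 = 31.25%; 0.26 to 0.44 per group.

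If every leaver exited in an open window, the figure would be the full 0.84 to 1.40 per group. That is the ceiling under this drop-out rate.

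**Step 5. Effect of one missed event.** The plan's own bounds in section 14.2.1 come first. For 0 of n, the Clopper-Pearson two-sided 95% upper limit is 1 − 0.025^(1/n).

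- n = 28: 0.1234 (plan 0.12).
- n = 112: 0.0324 (plan 0.03).

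Both reproduce. With one event:

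- 1/28 = 3.6%, interval 0.0009 to 0.1835.
- 1/112 = 0.9%, upper limit 0.0487.

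If the only event in a group of 28 is missed, the upper limit falls from 0.1835 to 0.1234 when the leaver stays in the denominator, or to 0.1277 (0 of 27) when the leaver is dropped. This shows scale only. It does not predict that such a case will occur.

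**The case against.** The strongest reply is that the ET visit is not empty. Interim history covers the time since the previous visit (section 7.2), concomitant medications are recorded with reasons for use (section 9.1.5), and a general examination and safety laboratory tests are done. This stands, and it rules out the reading that no adverse event assessment takes place at exit. It does not close the gap. Interim history is neither the structured interview for the 17 solicited terms (5 local, 12 systemic) nor the open adverse event question of section 9.1.

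A reader might also infer that events causing withdrawal are lost. The documents do not support that. Section 12.3 requires every effort to document the reason for leaving, and section 12.2 keeps volunteers whose vaccinations stop because of an adverse event in follow-up. What can go unrecorded is the grading and causality of such an event, and any event that was not the reason.

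A further tempting inference is that primary rates are biased downward, most of all in the most reactogenic regimen. Poor tolerability has its own route in section 12.1, stopping vaccination without leaving the study, and no protocol figure gives the direction or size of any bias. The endpoints also count volunteers, so a leaver who already reported a qualifying event at Day 3 or 7 is already counted.

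Finally, the month 16 column lacks vital signs too. They are not an endpoint and are not taken at the Day 3, 7 or 14 visits, so nothing is lost there.

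**Conclusion.** The point holds in a limited form. Followed as written, the schedule conflicts with two primary safety endpoints for anyone who exits in an open window, because a visit that does take place omits the two rows those endpoints depend on. This is a stated rule, not detail left to a statistical analysis plan.

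The loss is confined to structured, graded and causality-assessed collection of solicited and non-serious unsolicited events since the last attended visit. Its size is unknown and probably small: about 0.16 to 0.26 vaccinees per group in an open 28-day window, under the assumed 3 to 5% drop-out and even spread of exits. Exits clustered after doses would raise this; leavers who skip the ET visit or have no new qualifying event would lower the number who matter. About one leaver per group would require nearly all leavers to exit in an open window, which nothing in the protocol supports. The change is worth making because it is almost free and one event is visible in a group of 28.

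**What to change.** In Appendices A to C, either split the M16/ET column or add a footnote to it, so that the ET visit:

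- marks Adverse Events, covering all events since the last attended visit, when ET occurs before the last scheduled collection at D252;
- marks Local and Systemic Reactogenicity, with memory card review, when ET falls within 14 days of a dose.

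Add one matching sentence to section 12.3. The D252 limit keeps leavers on the same footing as completers, for whom non-serious events are not collected after that visit. Vital signs need not be added.

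The cost is a footnote or column in three tables, one sentence, and a few minutes of interview at a visit already being held. No extra visit or blood sample is needed, and no dose or treatment rule changes.

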# 13.0 DATA HANDLING

## 13.1 Data Collection and Record Keeping at the Clinical Research Centre

Data Collection: All study data will be collected by the clinical study staff using designated source documents and entered onto the appropriate case report forms (CRFs). CRFs will be provided by IAVI and should be handled in accordance with the instructions from IAVI. All study data must be verifiable to the source documentation. A file will be held for each volunteer at the clinic(s) containing all the source documents. Source documentation will be available for review to ensure that the collected data are consistent with the CRFs.

All CRFs and laboratory reports will be reviewed by the clinical team, who will ensure that they are accurate and complete.

Source documents and other supporting documents will be kept in a secure location.

Standard GCP practices will be followed to ensure accurate, reliable and consistent data collection.

Source documents include but are not limited to:

- Signed Informed Consent Documents
- Dates of visits including dates of vaccinations
- Documentation of any existing conditions or past conditions relevant to eligibility
- Reported laboratory results
- All adverse events
- Concomitant medications
- Local and systemic reactogenicity events

## 13.2 Data Collection and Transfer at the Human Immunology Laboratory

Immunogenicity data generated at the CRCs, IAVI Human Immunology and GSK Laboratories will be entered or transferred into the Laboratory Information Management System (LIMS) and then transferred directly to the DCC by the designated party according to the Laboratory Analytical Plan (LAP). Immunogenicity data generated by GSK Laboratories will be transferred directly to the DCC in a suitable format

## 13.3 Data Entry at the Clinical Research Centre

The data collected at the CRC will be entered onto the CRFs by the study staff. To provide for real time assessment of safety, data should be entered as soon as reasonably feasible (e.g., within one week) after a visit. Immunogenicity results will be transferred within 2 weeks after the assay is performed.

## 13.4 Data Analysis

The data analysis plan will be developed and agreed upon by the sponsor, GSK and the Principal Investigators. The statistician at the Data Coordinating Centre in collaboration with the Principal Investigator and the Sponsor will create tables according to this data analysis plan.

The DCC will conduct the data analysis and will provide interim and final study reports to the sponsor who will share the report with GSK, the principal investigators, the SRB and the regulatory authorities as appropriate.

# 14.0 STATISTICAL CONSIDERATIONS

### 14.1 Sample Size

A total of 140 volunteers (28 vaccine/7 placebo per group) will be entered into each of the 4 groups scheduled to receive F4co (formulated in  $AS01_B$  or  $AS01_E$ ) vaccine or placebo and Ad35-GRIN vaccine or placebo.

## 14.2 Statistical Power and Analysis

The small sample size is appropriate for an exploratory study of a novel product while safety, tolerability and immunogenicity of the vaccine combinations are investigated.

For safety and immunogenicity analyses, the placebo recipients from Groups A, and B will be combined.. However, for analyses where the schedule is not expected to have an impact, all placebo groups will be pooled together.

## 14.2.1 Safety and Tolerability

The rate of local and systemic reactogenicity will be used to assess the safety of the Investigational Products and proposed schedules.

The rate of Serious Adverse Events related to the Investigational Product will be used as one measure of the safety of the Investigational Products. Adverse Events that may be temporarily incapacitating (for example, loss or cancellation of work or social activities), which could make an Investigational Product impractical for large scale use if they occur in more than a small proportion of cases, will also be assessed.

All adverse events will be reported, grouped as to whether or not they qualify as SAEs, their severity assessment, and their relationship to the Investigational Product (as judged by the investigator).

The proportion of volunteers in each group who develop HIV infection will be analyzed.

### **Power Considerations**

For Grade 4 (very severe) adverse events related to Investigational Product: if none of the volunteers receiving the combination of Investigational Products experiences such reactions, the 2-sided 95% upper confidence bound for the rate of these adverse events in the population is 0.03 (n=112) and 0.12 (n=28), by the Clopper-Pearson method.

There is limited power for comparison of event rates between treatment arms. For example, with 80% power, the minimum detectable differences in event rates between the placebo (p) arm and the vaccine (v) arms are 50% (when  $n_p=7$ ,  $n_v=28$ ) and 28% (when  $n_p=14$ ,  $n_v=56$ ), assuming a one-percent incidence rate in the placebo arm (one-sided Fisher's exact test with significance level of 0.05).

## Planned Statistical Analyses:

Considering the low power available for group comparison and the associated risk of false safety signal in the context of multiple exploratory analyses, the analysis of safety events will be based on within-group descriptive summaries for the incidence rate of each event. The associated 95% confidence intervals for the incidence rate within each group will also be provided.

Interim analyses of grouped data will be carried out without unblinding the study to investigators or volunteers. At 1 month after the end of the vaccination regimen and at the end of the study, an analysis will be performed according to a pre-specified statistical analysis plan.

## 14.2.2 Vaccine Immunogenicity

Cellular immune responses will be analyzed using binomial methods to examine for the presence or absence of HIV specific T-cell responses quantified by ELISPOT and ICS. In addition, ICS magnitude will be analyzed based on log-normal distribution assumptions.

The Geometric Mean Titer (GMT) of anti-HIV antibodies will be assessed and the presence or absence of antibodies analyzed using binomial methods.

## Response Criteria for Immunogenicity Endpoints:

**IFN-** $\gamma$  **ELISPOT**: Responses are expressed as spot forming cells/million (SFC/10^6) PBMC. The GRIN peptides matching the Ad35 vaccine have been qualified using 55 seronegative PBMC specimens. Positive responses are defined as: 1) A Mock-subtracted response greater than 38 SFU/10^6 PBMC across all peptides 2) Mean replicate count >4x mean Mock count 3) Coefficient of Variation among replicate counts ≤70% 4) At least 3 replicates 5) Acceptance criteria for each sample comprises of the following; the average background < 50 and a response to PHA must be present. Peptides matched to the F4co vaccine will be qualified to determine a similar cut-off for the IFN- $\gamma$  ELISPOT.

**IL-2 ELISPOT:** A cut-off for the IL-2 ELISPOT will be assessed after qualifying the assay with GRIN and F4co peptides and/or F4co proteins. Cut-offs based on pre-vaccination responses may also be used.

**ICS**: ICS data are expressed as antigen-specific CD4+ CD40L+T-cells per million CD4+ T-cells or per hundred CD4+ T-cells (percentage). The

frequency of antigen specific CD4+ CD40L+ T cells are calculated as the difference between the frequency of CD4+ CD40L+ T cells expressing immune markers (among IFN- $\gamma$ , IL-2 and TNF- $\alpha$ ), upon in vitro stimulation with the peptide pools minus the frequency of CD4+ CD40L+ T cells expressing these immune markers upon in vitro stimulation with medium only. Differences less or equal to zero are imputed to 1 antigen specific immune marker expressing CD4+ CD40L+ T cell per 10^6 CD4+ T cells. The Geometric Mean calculations are performed by taking the anti-log of the mean of the log transformations. Frequency of CD4+ CD40L+ T-cells expressing markers to the fusion protein F4co (all antigens) is estimated by adding individual frequencies of CD4+ CD40L+ T-cells to each of the 4 antigens (p17, p24, Nef, RT). A responder is a subject with antigenspecific CD4+ response greater than or equal to the cut-off value. The cut-off will be chosen on the basis of pre-vaccination response for all subjects, by examining percentiles (95th percentile) in response to the different antigens.

Likewise ICS data are expressed as antigen-specific CD8+ T-cells per million CD8+ T-cells or per hundred CD8+ T-cells (percentage). Calculation of the frequencies of antigen specific CD8+ T cells and definition of a responder are both based on the same rules as for the antigen specific CD4+ T cells responses.

Anti-HIV antibody ELISA: IgG antibody responses to the fusion protein F4co and to the p24, RT, p17 and Nef antigens are assessed using standard ELISA techniques. A seropositive subject is a subject whose titre is greater than or equal to the cut-off value. The cut-off values for p17, p24, RT, Nef and F4co antibodies is 187 mEU/ml, 119 mEU/ml, 125 mEU/ml, 232 mEU/ml, and 42 mEU/ml, respectively. The seropositivity rate is defined as the percentage of seropositive subjects. Geometric Mean Concentrations (GMCs) are calculated by taking the anti-log of the mean of the log value transformations. Antibody values below the cut-off of the assay are given an arbitrary value of half the cut-off for the purpose of GMC calculation.

Ad35 neutralization titre: Ad35 Neutralization titre is measured in volunteers' serum using a qualified cell based assay. In this assay target A549 cells (human lung carcinoma) are infected with a pre-determined amount of Luciferase-encoding Ad35 virus in the presence of serially diluted volunteer's serum. Luciferase activity is measured after 48h of incubation and neutralization titre is inferred by plotting luciferase activity over serum dilution (or titre). From this plot we measure the inhibitory concentration at which 90% of the Ad35 infection is inhibited (EC90). If EC90 is inferior to 1/16 serum dilution the volunteer is considered Ad35 neutralization negative. Volunteers for which EC90 is equal or greater than 1/16 are considered positive.

